3.2 Efficacy

Outcome assessments will primarily be made at baseline, one, and three months post procedure for patients receiving either the active treatment or sham procedure. Clinical assessments of pain will be made at all clinic visits.

Primary outcome: **safety** as assessed from adverse event reporting and MRI evaluation

Primary efficacy outcome measure will compare the change of **WORST** pain experienced in 24 hours before and at 3 months following bilateral FUS medial thalamotomy versus sham procedures as determined from the 11-point numeric pain rating scale.

Secondary outcome measures will include other patient-reported outcomes including the Global Impression of Change and the Pain Domain from the PROMIS Inventory including items for intensity, quality, behavior and interference.

Imaging assessments will be obtained before and after treatment. The location and precision of the treatment, as well as the volume of the lesion, will be determined from pre- and posttreatment MRI at baseline, 1 day, 1 week, 1 month and 3 months. Functional imaging assessments with Dynamic 2-[¹⁸F] fluoro-2-deoxy-D-glucose Positron Emission Tomography (FDG PET) will be obtained at baseline and three months for each patient. Functional imaging will serve as an objective measure to correlate with clinical pain assessment.

A summary of outcome measures is listed:

Primary (efficacy) outcome: 11-point numeric pain rating scale NPRS (“worst” NPRS score over 24 hours). The change in pain rating from baseline to 3 months posttreatment will be determined and compared between treatment and control cohorts.

Secondary outcomes:

Patient-reported outcome measures:

- PROMIS scale v1.0 – Pain Intensity 3a
- PROMIS scale v2.0 – Neuropathic Pain Quality 5a
- PROMIS scale v2.0 – Nocioceptive Pain Quality 5a
- PROMIS scale v1.0 – Pain Behavior 7a
- PROMIS scale v1.0 – Pain Interference 8a
- Patient Global Impression of Change, 7 point

Functional imaging assessments:

- Dynamic FDG PET

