g. A comprehensive assessment of pain symptoms, functional limitations, and comorbid mood issues will be made by licensed pain psychologist. The evaluation consists of a clinical interview, as well as questionnaires/assessment tools that address mood and identify potential biopsychosocial factors that may contribute to the patient's pain experience. The Patient Health Questionnaire (PHQ-9) identifies potential depressive symptoms and the Generalized Anxiety Disorder 7-Item Scale (GAD-7) addresses anxiety. Additionally, the Pain Catastrophizing Scale (PCS) is helpful in recognizing a patient's tendency toward catastrophic thinking that is likely to negatively impact surgical or other invasive interventions' outcomes. Lastly, the Brief Battery for Health Improvement 2 (BBHI-2) is a psychometrically sound instrument that is normed on patients with pain and provides objective information related to underlying pain-related issues that are biopsychosocially related. Standard screening for pain procedures includes assessments of anxiety and mood:

- GAD-7
- PHQ-9
- PCS
- BBHI-2

h. Evaluation by a pain management physician.

i. CT Imaging: For the purpose of this study, the CT Exam should be an Axial scan with bone filter, an image resolution of 512x512, and image thickness of 1mm with zero (0) spacing

j. MR Imaging: For the purpose of this study, unenhanced MR Exams will be performed and include: volumetric MPRAGE, axial and coronal T2-weighted sequences, and axial and coronal diffusion-tensor imaging (DTI)

k. Once all items required for eligibility are completed, the principal investigator will review and sign eligibility or document the screen-failure. If at this point it is determined that the subject **does not** meet all Inclusion and Exclusion criteria and cannot be treated, the subject will be removed from the study. These subjects will be considered screening failures, and will not be included in any of the safety or efficacy endpoint analyses.

l. If the subject is deemed eligible for the study based on the screening criteria, then the following will be scheduled:

- Presurgical evaluation by the anesthesiology team
- Baseline assessments including Dynamic FDG PET imaging using the following process
 - a. Placement of IV catheter

- b. Slow injection with ~10 mCi of the FDG tracer via the catheter
- c. Imaged using the PET/CT scanner for 60 minutes starting at injection

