9. The half-spherical helmet containing the elements of MRgFUS transducer will be positioned around the subject's head in the treatment position. This should be done according to measurements taken from the pre-operative/imaging session(s).
10. A rubber diaphragm will be attached to the subject's head and to the transducer to create the acoustic coupling system between the ultrasound transducer and the scalp.
11. The immobilization system will be secured over the subject head to maintain a constant relationship between the target and the transducer.

12. A localizer scan (quick T1) and a non-contrast T2-FSE MR scan will be obtained to allow further refinement of the position the MRgFUS transducer focal point with respect to the targeted zone.
13. The interface within the rubber diaphragm will then be filled with degassed water. This volume will be completely filled with care to avoid air bubbles between the face of the transducer and the scalp. Through active circulation and cooling system, the water will be maintained chilled throughout the procedure to avoid undesired heating of the scalp and skull.
14. A series of MR images will be acquired to identify the target area, and plan the actual treatment
 - T2 Weighted imaging exam along at least 2 axes: Axial and Coronal
 - Other MR imaging series may also be acquired
15. The pre-therapy MRI and CT image datasets will be registered to the T2 weighted MR images that were just acquired. This image fusion of pre-operative MR assists in the accurate delineation of the target area and determination of a safe sonication pathway
 - The fusion of the CT data is required for the computation of phase correction values to correct for skull aberration, and identification of intracranial calcifications
 - Scars of the scalp will be designated to ensure the ultrasound beam avoids these specific areas
16. The treatment volume and plan will be defined by the neurosurgeon. The MRgFUS system will automatically compute the number of sonifications, and the (per sonication spot) phase and amplitude corrections necessary for the system to produce a focal spot at each of the desired locations.
17. An intravenous line will be maintained throughout the procedure. Noninvasive blood pressure, systemic arterial oxygen saturation, electrocardiogram, and end-tidal carbon dioxide will be monitored throughout the MRgFUS treatment using standard MRI-compatible monitoring devices.

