 - d. The titration of escalating focal sonifications will continue up to 60°C within a 5 mm diameter centered on CL, or until potential side effects are reported by the subject or observed by the clinical team.
 - e. The MRgFUS system is equipped with Stop Sonication Buttons: one for the subject to utilize, one for the nurse/anesthesiologist, and one for the treating physician to use. Hence, in the event of discomfort or pain, the subject will have the ability to abort the sonication at any time by activating the Stop Sonication Button. Once this button is activated, the system will instantly stop the energy delivery. The same thing will happen in the event the treating physician or the nurse activates their button. After addressing the subject concerns or discomfort, the procedure may continue without further delay. All adverse events that may be caused by these potential activation(s) of the Stop Sonication Button will be captured on the CRFs.

20. The physician may decide to terminate the sonication procedure at any time. For example for any of the following reasons:

- a. the subject's wish to terminate due to pain, severe discomfort, or any other reason,
- b. development of focal neurological deficits,
- c. occurrence of seizures,
- d. MRI signs of intracranial bleeding or significant brain swelling
- e. targeting difficulties, due to subject motion,
- f. inability to observe the focal point during sonication,
- g. inability to communicate with the subject
- h. any other medically indicated reason

21. After the procedure, an initial series of T1 or T2 weighted MR images will be acquired along two planes to assess the early treatment effects. Comprehensive MR imaging is obtained the following day with a head coil to optimally characterize the lesion. This will include: T1, T2, SWI, DWI, and DTI.

In the event of new neurological deficits or seizures are observed, other imaging modalities (including CT) should be performed immediately in addition to neurological and physical examinations.

22. The subject will be removed from the ExAblate table and taken to the hospital for recovery and neurological observation until the next morning. The neurosurgeon will evaluate the subject's neurological status and make a decision whether or not to discharge the subject. Subjects who are found to be neurologically unstable will remain in the hospital until the neurosurgeon determines it is medically indicated to discharge.

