6.7 Follow-up

Subject follow-up will be completed at Day 1, Day 7, Month 1, and Month 3 for all subjects who underwent CL lesioning/ablation using ExAblate system. Subject follow-up will be similar for those who underwent sham treatment. At 3 months, subjects who had sham treatment will be unblinded and offered MRgFUS.

Subjects will be evaluated at all follow-up visits for general health, neurological changes and efficacy measurements as well as for device/procedure related adverse events that may have occurred during the follow-up period. Medication regimen and PRN usage will be recorded at each follow-up along with the following assessments:

6.7.1 Day 1

- Evaluation of general health and neurological changes
- NPRS (Worst pain in 24 hrs)
- PROMIS
- Assess patient blind
- Assess safety and update adverse events as needed
- Review medications and record any changes
- MRI

6.7.2 Day 7

- Evaluation of general health and neurological changes
- NPRS (Worst pain in 24 hrs)
- PROMIS
- PGIC
- Assess patient blind
- Assess safety and update adverse events as needed
- Review medications and record any changes
- MRI

6.7.3 Month 1

- Evaluation of general health and neurological changes
- NPRS (Worst pain in 24 hrs)
- PROMIS
- PGIC
- Assess patient blind
- Assess safety and update adverse events as needed
- Review medications and record any changes
- MRI

6.7.4 Month 3

- Evaluation of general health and neurological changes
- NPRS (Worst pain in 24 hrs)
- PROMIS
- PGIC
- Assess patient blind
- Neuropsychological Pain Assessment
- GAD-7
- PHQ-9
- PCS
- BBHI-2
- MRI

- Dynamic FDG PET
- Assess safety and update adverse events as needed
- Review medications and record any changes
- Evaluation by a pain management physician

All pre-treatment and post treatment MR images will be de-personified (i.e.: subject identifiers made anonymous), archived and sent to InSightec. These analyses will also include full radiological assessments from baseline through all follow up visits.

In this study, subjects who use alternative treatments (not including medication change) during the 3-month follow-up period will be exited from the study, after completing required study examinations. The reason(s) for study exit will be noted on the Case Report Forms.

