- There is a risk of cavitation in the tissue at the focal point. Cavitation is the collapse of rapidly developed gas bubbles at the focal point due an extreme intensity of ultrasound excitation. This rapid collapse could cause high pressure, shock waves, and high temperatures. All systems are now equipped with cavitation detectors.
- There is a risk of blood brain barrier (BBB) disruption, edema, swelling, hemorrhage outside and remote to the targeted area. These events may theoretically occur due to heating effects (ie secondary hot spots) and or to the pressure wave of the ultrasound beam. The secondary hot spots risks are discussed below. To address the risks due to pressure waves of the ultrasound beam path, the system has been designed to be well below the "pressure wave threshold" that may trigger events of this nature. In all cases, thermal and regular imaging will be continuously assessed during the procedure. Finally, the subject(s) is continuously monitored by the anaesthesiologist (or nurse anaesthetist) during the ablation procedure for any change in the subject condition.

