9.11 Criteria for Stopping the Study

The study will be stopped for evaluation should:

1. any death occur, or
2. if two or more subjects experience
 - a. a cerebrovascular hemorrhage
 - b. or serious related neurological adverse event
 - c. or a 50% increase in pain from Baseline following two consecutive visits starting from 7-days post treatment visit.

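### SWI is specified for the Day 1 MRI but not before treatment, so subjects randomised first to thalamotomy have no required same-sequence scan to show whether an off-target focus is new

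*Protocol*

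**What the plan says.** **Before treatment.** Protocol 6.3 item 3j: "unenhanced MR Exams will be performed and include: volumetric MPRAGE, axial and coronal T2-weighted sequences, and axial and coronal diffusion-tensor imaging (DTI". SWI is not in the list. The same section requires a head CT with bone filter. The schedule in 7.0 shows no other MRI visit before the procedure. On Day 0, 6.5 steps 12 and 14 call for a quick T1 localiser and T2 imaging, and then leave the rest open: "Other MR imaging series may also be acquired".

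**After treatment.** For the comprehensive scan on the day after the procedure, 6.5 step 21 says "This will include: T1, T2, SWI, DWI, and DTI". Section 6.7 lists MRI at Day 7, Month 1 and Month 3 without naming sequences.

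**What the images are for.** Section 3.2 makes safety the primary outcome, "as assessed from adverse event reporting and MRI evaluation". On image handling, 6.7 states: "These analyses will also include full radiological assessments from baseline through all follow up visits". Section 9.4 names, among the risks, "hemorrhage outside and remote to the targeted area". Section 9.11 stops the study for evaluation "if two or more subjects experience" one of three listed events, the first being "a cerebrovascular hemorrhage".

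**The concern.** The protocol plans to read the images from baseline onward, but one of the sequences read after treatment has no required counterpart before it. SWI is the sequence in these lists that is sensitive to blood products. A bleed inside the planned lesion needs no baseline scan to be attributed to treatment. A focus away from the target does, because it could be an old micro-haemorrhage or a new event of the kind 9.4 warns about.

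Old foci are possible under the entry criteria. Age runs to 75. Facial trauma is an accepted cause of the pain (2.2), and the failed procedures that establish eligibility in 5.2 item 6 include microvascular decompression and intracranial partial sensory rhizotomy.

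The error can go either way. An old focus may be recorded as a treatment haemorrhage, or a new remote one may be set aside as old. Once a subject has been ablated, the missing scan cannot be obtained.

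**Working it through.** The protocol states no figure on this point, so there is none to reproduce. The check has two parts.

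**1. Imaging lists side by side**

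| Scan | Required sequences | SWI required? |
|---|---|---|
| Screening MRI (6.3 item 3j) | MPRAGE, T2, DTI | No |
| Day 0, before sonication (6.5 steps 12 and 14) | T1 localiser, T2; others optional | No |
| Day 1 (6.5 step 21) | T1, T2, SWI, DWI, DTI | Yes |
| Day 7, Month 1, Month 3 (6.7) | MRI, sequences not named | Not stated |

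**Who is affected**
- Ten subjects are allocated 1:1 (8.4), so about 10 × 1/2 = 5 are treated first.
- The other 5 or so have a sham procedure with no energy delivered (6.2, 6.6) and a Day 1 MRI (6.2, 7.0). Those who cross over return to Day 0 (7.0, footnote 1), with that SWI already on file before any ablation.
- The gap in individual comparison therefore concerns the first-treated group of about 5.

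**2. Illustration of size**

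Assumptions, none of them from the protocol:
- A proportion p of eligible subjects has at least one old SWI focus, with p = 5%, 10% or 20%.
- Subjects are independent.
- Every such focus is counted as a haemorrhage.

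With n = 5:

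P(at least 1) = 1 − (1 − p)^5

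P(at least 2) = 1 − (1 − p)^5 − 5p(1 − p)^4

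| p | (1 − p)^5 | 5p(1 − p)^4 | P(at least 1) | P(at least 2) |
|---|---|---|---|---|
| 5% | 0.7738 | 0.2036 | 22.6% | 2.3% |
| 10% | 0.5905 | 0.3281 | 41.0% | 8.1% |
| 20% | 0.3277 | 0.4096 | 67.2% | 26.3% |

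**Effect of one misclassification on the haemorrhage proportion**
- 1/5 = 20 percentage points in the first-treated group.
- 1/10 = 10 percentage points if every sham subject crosses over and all treated subjects are pooled.

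**The case against.** A reader might infer that Day 1 findings have no pre-treatment comparator at all. The documents do not support that. Every subject has baseline MPRAGE, T2, DTI and CT, and a T2 immediately before sonication. The baseline list is also worded so that SWI is not excluded. What is missing is a required scan with the same sequence.

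A reader might also infer that the stopping rule depends on SWI, and that all 10 subjects are at risk of triggering it falsely. On the same assumed prevalences, n = 10 would give 8.6%, 26.4% and 62.4% for two or more. Neither step holds:
- Section 9.11 mentions neither MRI nor SWI, and its consequence is a stop for evaluation. Under 10.1 a safety board judges whether each adverse event is related.
- A focus in a sham subject cannot be a treatment haemorrhage, because no energy was delivered and the treatment team knows the assignment (6.4). The relevant denominator is about 5.

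Other points on this side:
- The stated aim of the Day 1 scan is to characterise the lesion, not to search for remote bleeding. That is true, but 3.2 and 6.7 bring MRI into the primary safety assessment without restricting it to the target.
- The sham arm gives a concurrent Day 1 SWI reference of about 5 against 5. This stands as a group comparison, but it cannot date a focus in one first-treated subject.
- Exclusions for severe hypertension, bleeding-risk medication, neurological disease and coagulopathy (5.3 items 10, 12, 15 and 17) may lower the prevalence of old foci. Exclusion 24 can be read more or less broadly. This is why the prevalence is shown only as an assumed range.
- The analysis is descriptive (8.0), so no test or stated figure is affected. That limits the consequence but does not remove it, because a descriptive safety count in so few subjects depends on each classification being right.

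**Conclusion.** The point holds as a specification gap of modest size. Followed as written, the protocol gives first-treated subjects SWI only after ablation, so an off-target SWI focus in any of them can be dated only indirectly, from other sequences and CT. About 5 subjects are affected.

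The probabilities of about 2%, 8% and 26% for two or more old foci counted as haemorrhage among those 5 rest on assumed prevalences. They also take the worst case, in which every old focus is misread and counted. They illustrate scale and do not predict the stopping rule's behaviour. The shift of 20 points of 5, or 10 points of 10, per misclassified subject is plain arithmetic.

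That SWI shows old blood products which the baseline sequences may miss is general imaging knowledge and is not stated in the protocol. DWI is also named for Day 1 and not for baseline, but this is secondary because baseline DTI is already diffusion imaging.

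**What to change.** - In 6.3 item 3j, add SWI to the screening MRI, acquired with the same parameters as the Day 1 scan.
- In the primary safety outcome, report MRI haemorrhage as new or enlarged relative to that baseline SWI.
- Reconcile the wording of the haemorrhage criterion in 9.11 with the MRI safety assessment in 3.2 and 6.7, so that it is clear how the two relate. The content of the stopping rule is for the sponsor and investigators to decide.
- Adding DWI at baseline is optional.

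The cost is a few extra minutes in an MRI session every subject already has, with no contrast agent, new visit or new procedure. The change must be in place before a subject is treated, since the scan cannot be recovered afterwards.

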6.4 Randomization

Randomization occurs at the start of the focused ultrasound procedure, immediately prior to the first sonication. Subjects will be randomized in a 1:1 fashion to receive either a sham procedure, where the acoustic power is disengaged, or a bilateral medial thalamotomy. The treatment team (neurosurgeon and clinical research coordinator) will be aware of the treatment assignment. The assessment team (pain management specialist, pain psychologist, and nuclear medicine radiologist who interprets PET) and the subjects will be blinded throughout the three month study period. Subjects are unblinded at the end of the three month visit and sham subjects will be offered cross-over to treatment arm at that time.

6.5 Treatment Procedures

On the day of the treatment, the following clinical team members should be present:

Neurosurgeon: leads the planning and guidance of the treatment. They will also monitor the neurological performance and clinical status of the subject. They will be responsible for the overall management of the subject. The neurosurgeon will evaluate the subject's comfort level and direct sufficient sedation to maintain this comfort. Feedback of symptom relief is not expected to be necessary for this procedure.

The anesthesiologist or nurse anesthetist: they will monitor vital signs and provide necessary medications to keep the subject comfortable.

The overall treatment procedure steps will be performed as follows:

1. Subjects will be reminded to not take any anticoagulant (e.g. warfarin) or antiplatelet (e.g. aspirin) therapy in the week prior to and in the week after the focused ultrasound procedure.
2. The subject will be instructed not to eat or drink after midnight prior to the MRgFUS procedure, in order to permit the use of immediate general anesthesia in case of a treatment complication that may require emergency intervention.
-
3. Medications will be reviewed to confirm regimen is unchanged since study enrollment. Record prescribed and PRN medication usage.
4. An IV line will be positioned for the delivery of fluids and any medications required during the procedure. Some of the subjects may require a urinary catheter to keep the bladder empty during treatment. Noninvasive monitoring of heart rate, blood pressure, systemic oxygen saturation, electrocardiogram, and end-tidal CO₂ will be maintained throughout the procedure using standard MR-compatible monitoring devices.
 - The anesthesiologist or nurse anesthetist will administer appropriate medications for subject management if necessary. Since the medial thalamotomy procedure is image-guided and does not rely on intraprocedural feedback for targeting, intravenous sedation may be used as necessary for comfort. Subjects will not be intubated.
5. The subject's head will be carefully shaved and examined for pre-existing scalp scars or any other scalp lesions.
6. Graduated compression stockings will be worn to prevent deep venous thrombosis in the lower limbs.
7. The subject's head will be placed in the immobilization unit (similar to those used in stereotactic radiotherapy head fixation).
8. Subject will be positioned supine and headfirst on the MRgFUS therapy table.
9. The half-spherical helmet containing the elements of MRgFUS transducer will be positioned around the subject's head in the treatment position. This should be done according to measurements taken from the pre-operative/imaging session(s).
10. A rubber diaphragm will be attached to the subject's head and to the transducer to create the acoustic coupling system between the ultrasound transducer and the scalp.
11. The immobilization system will be secured over the subject head to maintain a constant relationship between the target and the transducer.

12. A localizer scan (quick T1) and a non-contrast T2-FSE MR scan will be obtained to allow further refinement of the position the MRgFUS transducer focal point with respect to the targeted zone.
13. The interface within the rubber diaphragm will then be filled with degassed water. This volume will be completely filled with care to avoid air bubbles between the face of the transducer and the scalp. Through active circulation and cooling system, the water will be maintained chilled throughout the procedure to avoid undesired heating of the scalp and skull.
14. A series of MR images will be acquired to identify the target area, and plan the actual treatment
 - T2 Weighted imaging exam along at least 2 axes: Axial and Coronal
 - Other MR imaging series may also be acquired
15. The pre-therapy MRI and CT image datasets will be registered to the T2 weighted MR images that were just acquired. This image fusion of pre-operative MR assists in the accurate delineation of the target area and determination of a safe sonication pathway
 - The fusion of the CT data is required for the computation of phase correction values to correct for skull aberration, and identification of intracranial calcifications
 - Scars of the scalp will be designated to ensure the ultrasound beam avoids these specific areas
16. The treatment volume and plan will be defined by the neurosurgeon. The MRgFUS system will automatically compute the number of sonifications, and the (per sonication spot) phase and amplitude corrections necessary for the system to produce a focal spot at each of the desired locations.
17. An intravenous line will be maintained throughout the procedure. Noninvasive blood pressure, systemic arterial oxygen saturation, electrocardiogram, and end-tidal carbon dioxide will be monitored throughout the MRgFUS treatment using standard MRI-compatible monitoring devices.

NOTE: All procedures for both arms are the same to this point. Below is the description of treatment for ExAblate Arm. The Sham will be identical except that the energy will be turned to 0.

18. A central point in the targeted area will be targeted with a low dose, sub-lethal energy level sonication to confirm the targeting accuracy on the MR images. Focal point position and/or transducer location will be adjusted as necessary. The bilateral lesioning will be planned and executed as follows:

- a. Stereotactic planning of both (left and right) medial thalamic targets will be performed on the ExAblate Neuro workstation in the pre-planning phase. The central lateral thalamic nucleus CLT nucleus will be targeted by stereotactic coordinates in reference to the midcommissural point of the ACPC line.
 - b. If the pain symptoms are asymmetric or unilateral, the CLT nucleus contralateral to the most symptomatic side will be treated first. The acoustic energy will be escalated in a series of incremental sonifications until a therapeutic ablation of temperature of 60-65°C is reached by peak voxel, MR thermometry. The second, ipsilateral CLT target will then be treated with the same protocol.
 - c. If the pain symptoms are symmetric, the nondominant CLT will be treated first. The dominant side CLT will be treated as the second target.
19. To enhance the procedure safety and mitigate some of the inherent risks of thermal lesioning of brain tissue:
 - a. The thalamotomy treatment will be performed as a series of sonifications with small increments in power within the designated target volume.
 - b. The subject will be examined periodically by the clinical team for neurologic signs and symptoms.
 - c. Sonication will start with low energy prior to permanent thermal ablation. This is to ensure the planned sonication to be centered on the CL nucleus of the Thalamus. Low energy sonication will non-destructively warm the target. The warming will be captured by the MR thermometry and the MR thermal images will be displayed in real time to the treating physician. The physician will then verify that the warming is centered on the anatomic target. This will allow the centering of the eventual permanent thermal lesion in the correct location, in the center of the CL nucleus of the Thalamus.
 - d. The titration of escalating focal sonifications will continue up to 60°C within a 5 mm diameter centered on CL, or until potential side effects are reported by the subject or observed by the clinical team.
 - e. The MRgFUS system is equipped with Stop Sonication Buttons: one for the subject to utilize, one for the nurse/anesthesiologist, and one for the treating physician to use. Hence, in the event of discomfort or pain, the subject will have the ability to abort the sonication at any time by activating the Stop Sonication Button. Once this button is activated, the system will instantly stop the energy delivery. The same thing will happen in the event the treating physician or the nurse activates their button. After addressing the subject concerns or discomfort, the procedure may continue without further delay. All adverse events that may be caused by these potential activation(s) of the Stop Sonication Button will be captured on the CRFs.

20. The physician may decide to terminate the sonication procedure at any time. For example for any of the following reasons:

- a. the subject's wish to terminate due to pain, severe discomfort, or any other reason,
- b. development of focal neurological deficits,
- c. occurrence of seizures,
- d. MRI signs of intracranial bleeding or significant brain swelling
- e. targeting difficulties, due to subject motion,
- f. inability to observe the focal point during sonication,
- g. inability to communicate with the subject
- h. any other medically indicated reason

21. After the procedure, an initial series of T1 or T2 weighted MR images will be acquired along two planes to assess the early treatment effects. Comprehensive MR imaging is obtained the following day with a head coil to optimally characterize the lesion. This will include: T1, T2, SWI, DWI, and DTI.

In the event of new neurological deficits or seizures are observed, other imaging modalities (including CT) should be performed immediately in addition to neurological and physical examinations.

22. The subject will be removed from the ExAblate table and taken to the hospital for recovery and neurological observation until the next morning. The neurosurgeon will evaluate the subject's neurological status and make a decision whether or not to discharge the subject. Subjects who are found to be neurologically unstable will remain in the hospital until the neurosurgeon determines it is medically indicated to discharge.
23. Subject will be asked the "Patient Blinding Question" to determine whether or not they believe they had a sham or real procedure.

